## **7.8 Multicenter Studies**

Data will be pooled from all centers prior to analysis. Adjustments for different centers will not be performed.

## **7.9 Multiple Comparisons/Multiplicity**

The study is considered exploratory. Thus, the issue of multiplicity will not be addressed for statistical inferences.

## **7.10 Data Monitoring**

The Study Review Committee (SRC) will review ongoing safety data and any potential safety signals. Escalation to a new dose level may proceed only after the SRC conducts a review of safety data from all preceding subjects who are evaluable for DLTs.

The SRC will evaluate the accumulating safety data and advise if enrollment needs to be held at any time in a dose cohort for further safety evaluation.

# **8. STATISTICAL ANALYSIS**

Descriptive statistics for continuous data will include the number of observations (n), mean, standard deviation, median, minimum, first and third quartiles, and maximum. For discrete variables, descriptive analyses will be based on estimates of the number of subjects and related percentages. Unless otherwise stated, confidence intervals, when presented, are 2-sided with 95% confidence level.

All analyses will be performed using SAS® Version 9.4 (SAS Institute Inc., Cary NC).

## **8.1 Subject Disposition**

Subject disposition will be summarized for each dose cohort by tumor type, treatment regimen and in total for all enrolled subjects. In addition, subject disposition will be tabulated by tumor type and in total. The following categories of subject disposition will be included:

- Subjects who were enrolled
- Subjects who were treated
- Subjects who discontinued from the study
- Subjects who completed the study and were still alive at EOS visit

For subjects who discontinued from the study, the primary reason for ending the study will be summarized. Additionally, on-study deaths (defined as deaths during treatment period or within 30 days of treatment discontinuation) will be presented. The number and percentage of subjects in each defined analysis population will be tabulated as appropriate.

All deaths that occur on study will be reported in a subject listing, which will include the primary cause of death and the number of days between the date of the first (and last) dose of study drug and death.

All subject disposition data will be presented in a data listing.

## **8.2 Demographics and Baseline Characteristics**

Demographics and baseline characteristics will be summarized descriptively by tumor type, treatment regimen and in total based on the Safety Evaluable Set and the Efficacy Evaluable Set as appropriate. Sex, race, ethnicity, age group (< 65 years and ≥ 65 years), and baseline ECOG performance status will be summarized with contingency tables. Age at informed consent (years) and baseline weight will be presented with descriptive statistics.

Time from initial diagnosis of primary disease presented at enrollment (months) and the number of prior anti-cancer therapies (regimens) will be summarized using descriptive statistics.

Moreover, for subjects of B-Cell malignancy, DLBCL type (subjects with DLBCL only), status from last treatment of the primary disease (relapsed or refractory), status of tumor FDG avidity, nodal site involvement, cancer type (unilateral or bilateral), extranodal site involvement, TLS risk category, IgVH mutation status (subjects with CLL or SLL only), and interphase cytogenetic abnormality (subjects with CLL or SLL only) will be summarized to show the number and percentage of subjects in each category; for subjects of AML, status from last treatment of the primary disease (relapsed, refractory having received 2 lines of therapy, induction and salvage, relapsed from hematopoietic stem cell transplant), WHO classification (2016) if applicable, and 2017 ELN genetic risk criteria, will be summarized to show the number and percentage of subjects in each category, by treatment regimen (monotherapy and combination therapy) and in total.

At the same time, the number and percentage of subjects who had undergone prior cancer surgery, prior radiation therapy, prior transplants (and type of transplants), prior anti-cancer therapy (and best response to therapy) will be tabulated by tumor type and in total.

Information of subject-level demographic and baseline disease characteristics will be presented as data listings.

## **8.3 Medical and Surgical History**

Medical history will be coded using MedDRA Version 24.1

All data of medical history will be listed by subject.

## **8.4 Prior and Concomitant Medications**

Prior and concomitant medications as well as prior anti-cancer therapies will be coded using WHO-DDE B3 (March 2018). Prior medications/therapies include those that were taken prior to and stopped before the first dose of the study drug. Concomitant medications include the ones taken on or after the first dose date of the study drug. Prior and concomitant medications will be tabulated by Anatomical Therapeutic Classification (ATC) and preferred term (PT) by tumor type, treatment regimen and in total for the Safety Evaluable Set.

The subject-level data listings for prior and concomitant medications as well as prior anti-cancer therapies will be presented.

## 8.5 Dosing Status and Duration of Treatment

The number and percentage of subjects who experienced dose adjustments (dose interruption, dose reduction, dose increase, or dose re-escalation), of subjects with missed doses, and of subjects who discontinued voruciclib will be tabulated for each dose cohort and in total by disease group. Reasons for dose modification will also be similarly tabulated.

Duration of treatment (DOT) will be summarized descriptively by dose cohort and in total. Additionally, the swimmer plot of DOT will be generated and grouped by dose cohort and tumor type. For subjects who either completed or discontinued the treatment by the EOS visit, DOT will be calculated as follows:

$$\text{DOT (months)} = (\text{Last Dose Date} - \text{First Dose Date} + 1) / 30.4375$$

All source data regarding study drug administration and study drug accountability log will be presented by subject-level data listings.

## 8.6 Efficacy Analyses

### 8.6.1 Primary Efficacy Analysis

Not applicable.

### 8.6.2 Secondary Efficacy Analysis

The secondary efficacy endpoints include the following:

- Overall Response Rate (ORR), defined as the proportion of subjects who achieve a best overall response of
  - CR, CRi, or PR, with responses defined per 2008 International Workshop on CLL (IWCLL) guidelines,
  - CR or PR by 2014 Lugano criteria for non-Hodgkin lymphoma,
  - CR, CRi, CRMRD, MLFS by the 2017 ELN criteria for AML
- Estimates of the exposure and association with efficacy variables for voruciclib administered as monotherapy, and for voruciclib and venetoclax when administered in combination
- Duration of Response (DOR) defined as the time from first achieving a response to date of documented disease progression or death from any cause
- Progression-Free Survival (PFS) defined as time from first dose of study drug to date of documented disease progression or death due to any cause

The efficacy analyses will be conducted on the Efficacy Evaluable Set.

#### 8.6.2.1 Overall Response Rate (ORR) and Rate of CR/CRi

ORR will be derived by calculating the proportion of subjects with best response of CR/CRi or PR by tumor type, treatment regimen and in total. Tumor responses will be determined by

the Investigator per International workshop on CLL guidelines (Hallek et al. 2008; see Appendix 4 in protocol) for CLL and SLL cancer type, by Lugano criteria (Cheson et al. 2014; see Appendix 5 in protocol) for the other Non-Hodgkin Lymphoma cancer types and by the 2017 ELN criteria for AML (Döhner 2017; see Appendix 4 in protocol). The procedure and requirement to confirm the CR/CRi or PR response will be followed per aforementioned guidelines and study protocol as well. The point estimate of ORR will be accompanied by 95% exact binomial confidence interval (CI) using the Clopper-Pearson method. Rate of CR/CRi will be summarized in the same manner as for ORR.

For subjects with measurable solid tumors, sum of the product of perpendicular diameters (SPD) will be computed by summing the products of the maximum diameter of a tumor and the largest diameter perpendicular to this maximum diameter (across all individual tumors). The baseline and the minimum post-baseline values of SPD as well as the best percentage change in the SPD from baseline will be calculated for subjects with measurable solid tumors. Waterfall plots will be used to depict graphically, grouped by tumor type, for individual subjects of their best percentage change from baseline with regards to SPD in target lesions.

All tumor assessment data (including liver/spleen assessment, target lesions, non-target lesions, and overall response assessment) will be listed by subject.

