A Phase 2 study of venetoclax monotherapy in 32 patients with AML (30 with relapsed and/or refractory; 2 newly diagnosed), demonstrated a 19% response rate (2 CR and 4 complete remissions with incomplete hematologic recovery [CRi]) with a median duration of response (DOR) of 48 days. Venetoclax was generally tolerated up to doses of 1200 mg daily (Konopleva 2016). In another study, venetoclax in combination with azacitidine or decitabine in 57 previously untreated elderly AML patients was administered at doses up to 1200 mg. No dose-limiting toxicities (DLTs) were observed, but subjects at the 1200 mg dose had frequent dose reductions due to gastrointestinal (GI) events. Overall, a 61% remission rate was obtained with 14/57 CR and 21/57 CRi (DiNardo 2018).

These data demonstrate that targeted therapy specific for the apoptotic pathway can have significant clinical benefit for patients with both B-cell malignancies and AML. However, despite high response rates, patients are not cured by currently approved therapy and will generally experience disease progression, indicating the need for development of new agents with a complementary mechanism of action that either alone or in combination with venetoclax or other agents enhance disease clearance and circumvent disease resistance.

Myeloid cell leukemia protein 1 (Mcl-1) is a member of the Bcl-2 anti-apoptotic, pro-survival family of molecules that are commonly over-expressed in B-cell malignancies and AML. Overexpression of Mcl-1 is associated with poor prognosis and resistance to therapy. Mcl-1 is not inhibited by venetoclax, which is specific for Bcl-2, and increased expression of Mcl-1 can be a mechanism of resistance for venetoclax therapy. Acquired resistance of lymphoma cell lines to Bcl-2 inhibition in vitro has been shown to involve transcriptional upregulation of Mcl-1 (Yecies 2010). Additionally, non-clinical studies have also demonstrated the ability of Mcl-1 to render AML cells resistant to Bcl-2 targeted agents, and have demonstrated synergy in AML models between agents targeting Bcl-2 with those targeting Mcl-1 expression including cyclin-dependent kinase 9 (CDK9) inhibitors (Pan 2015, Bogenberger 2017, Luedtke 2017).

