Only the tablet formulation containing the voruciclib malonate salt will be used in the voruciclib plus venetoclax combination group.

Table 3: Dose Cohorts with Combination Voruciclib + Venetoclax (Amendment 11)

Cohort Dose Level	Doses and Schedule
12	voruciclib 50 mg QOD, administered IS _{2w,2w} + venetoclax administered QD × 28 days
13	voruciclib 50 mg QD, administered IS _{2w,2w} + venetoclax administered QD × 28 days
14	voruciclib 100 mg QD, administered IS _{2w,2w} + venetoclax administered QD × 28 days
15	voruciclib 150 mg QD, administered IS _{2w,2w} + venetoclax administered QD × 28 days
16	voruciclib 200 mg QD, administered IS _{2w,2w} + venetoclax administered QD × 28 days
17	voruciclib 250 mg QD, administered IS _{2w,2w} + venetoclax administered QD × 28 days
18	voruciclib 300 mg QD, administered IS _{2w,2w} + venetoclax administered QD × 28 days
19	voruciclib 350 mg QD, administered IS _{2w,2w} + venetoclax administered QD × 28 days

Abbreviation: QOD = once every other day

At the completion of the DLT period for each cohort, decisions to escalate in subsequent cohorts will be guided by SRC review of all available safety data, PK and PD data.

For Cohort 12, the dosing of voruciclib will be Days 3, 5, 7, 9, 11, and 13 of Cycle 1, and Days 1, 3, 5, 7, 9, 11, and 13 of Cycle 2 and beyond.

Dose escalation to the next cohort will be initiated after 3 subjects have completed 1 cycle with no reported DLTs, or after 6 subjects have completed 1 cycle with no more than 1 DLT (as defined in [Section 4.4](#)) and with the approval of the SRC after review of safety from the cohort under review.

Intra-patient dose escalation to the next dose in Cycle 2 or later cycle is allowed at the discretion of the investigator and after consultation with the Sponsor if the next dose level has been declared safe by the SRC. More specifically, a subject enrolled at a dose level X may have their dose escalated to the next dose level X + 1 after completing Cycle 1 without a DLT.

Dose escalation proceeds until assessment of clinical and PK parameters by the SRC establishes the safe BED for voruciclib in combination with venetoclax. More specifically, a voruciclib dose in combination with venetoclax that meets the following criteria:

- DLT not to exceed 1 in 6 patients, overall response rate (ORR) $\geq 30\%$, as compared to historical ORR of 19% with 400-800 mg venetoclax alone in relapsed/refractory AML ([Konopleva 2016](#)), and

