10.2. Study Endpoints

The primary study objectives are to determine the safety and tolerability and safe and mBED of voruciclib monotherapy in subjects with relapsed and/or refractory B-cell malignancies and AML and to determine the safety, tolerability and safe and mBED of voruciclib in combination with venetoclax in subjects with relapsed and/or refractory AML.

Safety will be assessed by AEs graded according to NCI CTCAE v5.0; laboratory safety tests including hematology (CBC), serum chemistry; physical examination; vital signs; ECOG performance status; and triplicate 12-lead ECG. If 2 or more of 6 subjects experience a DLT in a dose cohort, then the next lower dose will be the MTD.

The primary endpoint is:

- The incidence of AEs, including DLTs.

Secondary endpoints are:

- Efficacy endpoints within each tumor type:
 - a. Overall Response Rate (ORR), defined as the proportion of subjects who achieve a best overall response of
 - CR, CRi, or PR, with responses defined per 2008 International Workshop on CLL (IWCLL) guidelines,
 - CR or PR by 2014 Lugano criteria for non-Hodgkin lymphoma,
 - CR, CRi, CR_{MRD}, MLFS by the 2017 ELN criteria for AML
 - b. DOR defined as the time from first achieving a response to date of documented disease progression or death from any cause. Subjects who die due to any cause prior to progression will be censored
 - c. PFS defined as time from first dose of study drug to date of documented disease progression or death from any cause
 - d. Estimates of the exposure and association with efficacy and safety variables for voruciclib administered as monotherapy, and the PK of voruciclib and venetoclax when administered in combination

The exploratory endpoints are:

- a. Effects on biomarkers and functional activities of proteins in the apoptotic pathway
- b. Correlations of anti-tumor activity and baseline tumor characteristics

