#### 5.1.2 Secondary Efficacy Endpoints

Secondary efficacy endpoints (within each tumor type: AML and B cell malignancies) are as follows:

- Overall Response Rate (ORR), defined as the proportion of subjects who achieve a best overall response of
  - CR, CRi, or PR, with responses defined per 2008 International Workshop on CLL (IWCLL) guidelines,
  - CR or PR by 2014 Lugano criteria for non-Hodgkin lymphoma,
  - CR, CRi, CRMRD, MLFS by the 2017 ELN criteria for AML
- Estimates of the exposure and association with efficacy variables for voruciclib administered as monotherapy, and for voruciclib and venetoclax when administered in combination
- Duration of Response (DOR) defined as the time from first achieving a response to date of documented disease progression or death from any cause. Subjects who die due to any cause prior to progression will be censored. DOR will be calculated as follows for subjects who have a best overall response of CR/CRi or PR:

$$\text{DOR (months)} = (\text{Progression/Censoring Date} - \text{Response Start Date} + 1) / 30.4375$$

Subjects meeting at least one of the following criteria will be right-censored for DOR:

- death due to any cause prior to disease progression
- subsequent anticancer therapy without documented disease progression
- alive and without documented disease progression on or before the EOS visit

If a subject meets more than one of these criteria, then the scenario that occurs first will be used for the analysis. The progression or censoring date will be determined based on the conventions listed in Table 5-1.

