### **6.3 Efficacy Evaluable Set**

The Efficacy Evaluable Set is defined as subjects who complete the first scheduled post-baseline efficacy evaluation (scheduled on C3D1 for B-cell lymphoma subjects and C2D1 for AML subjects) or develop progression of disease or death prior to the first scheduled post-baseline efficacy. The Efficacy Evaluable Set will be utilized for the analyses of efficacy.

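### The SAP derives AML response rate and duration of response from CR/CRi or PR, whereas the AML endpoint is CR, CRi, CR_MRD or MLFS; the response set behind the 30% mBED criterion is also not stated

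*SAP*

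**What the plan says.** **Endpoint.** Protocol 10.2 defines ORR disease by disease. For CLL it is CR, CRi or PR, and for lymphoma CR or PR. For AML the list is CR, CRi, CR_MRD and "MLFS by the 2017 ELN criteria for AML"; PR is not in it. SAP 5.1.2 and the opening of SAP 8.6.2 repeat these three definitions.

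**Derivation.** SAP 8.6.2.1 then gives a single rule: "ORR will be derived by calculating the proportion of subjects with best response of CR/CRi or PR by tumor type". AML is within its scope, since the same paragraph has responses judged "by the 2017 ELN criteria for AML". It makes no exception for AML. It also plans a separate CR/CRi rate, presented in the same way as ORR with an exact confidence interval.

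**DOR.** SAP 5.1.2 states: "DOR will be calculated as follows for subjects who have a best overall response of CR/CRi or PR".

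**Changes from the protocol.** SAP section 10 declares none.

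**mBED criterion.** For the combination, Protocol 4.3.2 (repeated in SAP 3.1.1) requires at most 1 DLT in 6, a trough concentration of 1 to 1.5 µM, and an ORR of at least 30%, "as compared to historical ORR of 19% with 400-800 mg venetoclax alone in relapsed/refractory AML". Protocol section 1 describes the source as a study of 32 patients that "demonstrated a 19% response rate (2 CR and 4 complete remissions with incomplete hematologic recovery" (CRi).

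**Population.** SAP 6.3 bases efficacy on "subjects who complete the first scheduled post-baseline efficacy evaluation", together with those who progress or die before it.

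**The concern.** The sentence in SAP 8.6.2.1 is the one a programmer will follow, and for AML it does not produce the endpoint that the protocol and the SAP's own endpoint sections define. Protocol Table 18 lists MLFS and PR as separate AML categories, so the two responder sets differ. DOR has the same fault: some endpoint responders would have no duration, and some endpoint non-responders would have one. With a nil return in SAP section 10, nothing tells the reader of the results which definition was used.

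ORR also appears in the criterion for the combination mBED, which is a primary objective. That criterion does not say which responses count or who is in the denominator, and the comparator is reported as CR and CRi only. The ORR set against 30% may therefore not be like for like with the 19%.

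**Working it through.** **Step 1: the definitions side by side, AML only.**

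| Best response | Endpoint (Protocol 10.2; SAP 5.1.2, 8.6.2) | ORR derivation (SAP 8.6.2.1) | DOR set (SAP 5.1.2) |
|---|---|---|---|
| CR, including CR_MRD | responder | responder | yes |
| CRi | responder | responder | yes |
| MLFS | responder | not counted | no |
| PR | not counted | responder | yes |

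In Protocol Table 18, CR without minimal residual disease is CR plus a negative marker, so its absence from SAP 8.6.2.1 loses nobody. The whole difference is MLFS against PR. For CLL the derivation equals the endpoint. For lymphoma it agrees in substance, because Protocol Table 22 has no CRi category. Only AML is affected.

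**Step 2: size of the discrepancy.** Let C be the number with CR or CRi, M with MLFS, P with PR, and n the group size.

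- Endpoint ORR = (C + M)/n
- Derived ORR = (C + P)/n
- Difference = (M − P)/n

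The smallest counts that reach 30% are 2 of 6 (0.30 × 6 = 1.8), 4 of 12 (3.6) and 6 of 18 (5.4). Six is a full escalation cohort, 12 the planned maximum expansion per schedule, and 18 their sum. The documents give no MLFS or PR rate, so these cases are illustrations:

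| n | C | M | P | Endpoint ORR | Derived ORR | CR/CRi only |
|---|---|---|---|---|---|---|
| 6 | 1 | 1 | 0 | 2/6 = 33.3% | 1/6 = 16.7% | 16.7% |
| 6 | 1 | 0 | 1 | 1/6 = 16.7% | 2/6 = 33.3% | 16.7% |
| 12 | 3 | 1 | 0 | 4/12 = 33.3% | 3/12 = 25.0% | 25.0% |
| 12 | 3 | 0 | 1 | 3/12 = 25.0% | 4/12 = 33.3% | 25.0% |
| 18 | 4 | 2 | 0 | 6/18 = 33.3% | 4/18 = 22.2% | 22.2% |

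One subject is enough at n = 6 or 12, and the shift can go either way. If M = P the two rates coincide, but the responders, and so the DOR sample, still differ.

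**Step 3: the comparator.** Inputs from Protocol section 1: 2 CR, 4 CRi, 32 patients (30 relapsed or refractory, 2 newly diagnosed).

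- (2 + 4)/32 = 6/32 = 18.75%, which rounds to the stated 19%.
- Exact (Clopper-Pearson) 95% interval: lower limit is the 2.5% point of Beta(6, 27) = 7.2%; upper limit is the 97.5% point of Beta(7, 26) = 36.4%.

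The 19% is thus fully accounted for by CR and CRi, and 30% lies inside its interval. The trial's endpoint adds MLFS to those categories and the SAP derivation adds PR. The criterion says which to use in neither document.

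**The case against.** **The sentence in 8.6.2.1 is generic and the endpoint sections govern.** It is generic, and it works for CLL and lymphoma. But it names the AML criteria in the same paragraph without an exception, and the DOR rule repeats the same set, so it cannot be put down to one loose phrase. Nor is it a lag behind a protocol amendment: SAP 5.1.2 itself carries the MLFS definition.

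**A like-for-like numerator is already planned.** This stands. SAP 8.6.2.1 provides a CR/CRi rate with an exact interval. What is missing is a version by dose in all treated subjects, and a pointer to it from the mBED criterion. SAP 7.7 and 8.6.2.1 present efficacy by tumor type, regimen and overall.

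**The link to dose selection is not shown.** This stands too. The Study Review Committee applies the 30% criterion in real time, and nothing says that it uses the SAP 8.6.2.1 derivation or the Efficacy Evaluable Set. A reader might infer that the SAP error feeds straight into the mBED decision; the documents do not establish that. ORR is also only one of three criteria, and no formal test is attached to it.

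**Upward bias.** A reader might infer that either trial ORR is bound to be inflated against the 19%. The protocol reports who responded in the cited study, not how that study defined response. Had it counted PR and seen none, the figure would still be 6/32. Nor is it stated whether the 32 were all treated or only evaluable patients, so a narrower denominator in this trial is unproven.

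**Drop-out allowance.** A reader might also apply the 10% (Protocol 10.1) or 20% (SAP section 4) allowance as a loss from the ORR denominator. That allowance covers failure to complete Cycle 1. Subjects who progress or die early stay in the Efficacy Evaluable Set as non-responders, so the allowance does not measure exclusions from ORR.

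**Conclusion.** The contradiction on AML ORR and DOR is plain from the text and needs correcting before the tables are programmed. It misclassifies every AML subject whose best response is MLFS or PR. The effect on ORR is (M − P)/n: 16.7 percentage points per subject at n = 6 and 8.3 at n = 12, in either direction. How many subjects will be affected is unknown, since no MLFS or PR rates are given.

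The mBED part is narrower and held with less confidence. The 30% criterion lacks a stated response set and denominator, and its comparator is reported as CR plus CRi in 32 patients. That warrants a clarification. It does not show that the trial's ORR is biased against the benchmark or that a wrong dose would be chosen, because the documents give neither the cited study's response definition nor the committee's method of computing ORR. Nor does it require the mBED to be labelled provisional: expansion cohorts and exact intervals are already planned.

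**What to change.** 1. In SAP 8.6.2.1, replace the single rule with disease-specific derivations. For AML, count CR, CR without minimal residual disease, CRi and MLFS. Keep CLL (CR, CRi, PR) and lymphoma (CR, PR) as in SAP 5.1.2.
2. In SAP 5.1.2, compute AML DOR for those same AML responders, and adapt the optional split by response type in SAP 8.6.2.2, which now contrasts CR/CRi with PR.
3. In Protocol 4.3.2 and SAP 3.1.1, state which responses and which subjects enter the ORR that is compared with 30%.
4. Add one table giving the planned CR/CRi rate, with its exact interval, for all treated AML combination subjects by dose and schedule, as the like-for-like comparison with the 2 CR and 4 CRi reported among 32.

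The cost is SAP wording, a clarifying sentence in the protocol and one table; no new data are needed. A rate on CR and CRi in all treated subjects may be slightly less favourable than the ORR as now planned.
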